10.3 Vital Sign Measurements

Systolic blood pressure (mmHg), diastolic blood pressure (mmHg), and pulse rate (bpm) will be assessed at analysis visits Screening, Baseline, Week 2, Week 4, and Last Post-Baseline Visit. Observed vital signs and changes from baseline will be summarized for the vital signs using descriptive statistics.

10.4 12-Lead Electrocardiogram (ECG)

Electrocardiogram (ECG) parameters will be measured at Screening, Baseline, and Week 4/Early Termination. Descriptive statistics of observed values and changes from baseline will be summarized for:

- ECG Mean Heart Rate (beats/min)
- RR Interval (msec)
- PR Interval (msec)
- QRS Duration (msec)
- OTcF Interval (msec)

QT Interval and QTcB Interval will be collected and provided in subject listings, but not included in the summary tables. The interpretation of 'Normal', 'Abnormal, not clinically significant', and 'Abnormal, clinically significant' will be summarized at each analysis visit. A shift table of these interpretations will be provided from baseline to Week 4 and Last Post-Baseline Visit.

Frequency distributions of the QTcF Interval will be displayed for abnormally high values that are greater than their baseline value at any post-baseline visit and the following data cuts:

- > 450 msec and > Baseline Value
- > 470 msec and > Baseline Value
- > 500 msec and > Baseline Value

Additionally, the change from baseline frequency distributions of the QTcF Interval will displayed for the following data cuts:

- > 30 msec
- > 60 msec

10.5 Physical Examinations

10.5.1 Complete and Brief Physical Examinations

A complete physical examination will be given to subjects at the screening visit. The following 8 pre-defined areas will be assessed with the option to examine other areas as well:

- HEENT (Head, Eyes, Ears, Nose, and Throat); Lymph Nodes; Respiratory; Cardiovascular; Gastrointestinal; Musculoskeletal; Dermatologic; and Extremities
- Additional Other Specified Areas (no specific limit)
 - The body system will be specified on the CRF and will be standardized in the subject listings.

Responses may be "Normal", "Abnormal", or "Not Done" for each of the 8 pre-defined areas. If another body system is entered on the CRF, only "Normal" or "Abnormal" responses will be collected. If any response was "Abnormal" then the abnormality will be specified on the CRF. If either all the assessments or individual assessments are marked as "Not Done" then the reason not done will be entered on the CRF.

A brief physical examination will be given at the Baseline, Week 4/Early Termination, and potentially during any unscheduled visits. The following question will be answered by the investigator, "Were there any clinically significant changes observed since the previous Physical Exam?" If the answer is "No" then no other data will be collected. For "Yes" responses, any specific body system(s) that changed will have the details entered on the CRF.

All complete and brief physical examinations will be provided in subject listings. An additional listing will be provided for any changes from normal to abnormal in any area that occurred at any post-baseline visit. No summary tables will be provided.

10.5.2 Neurological Examination

A complete neurological examination will be given to subjects only at the screening visit. The following 7 neurological areas will be assessed:

Cranial Nerves; Muscle Strength & Tone; Sensory Function; Coordination; Gait; Reflexes;
 and Mental Status

Responses may be "Normal", "Abnormal", or "Not Done" for each of the 7 neurological areas. If any response was "Abnormal" then the abnormality will be specified on the CRF. If either all the

assessments or individual assessments are marked as "Not Done" then the reason not done will be entered on the CRF.

Results collected will be presented in a subject listing, but not summarized in a table.

10.6 Other Safety Analyses

10.6.1 Sheehan Suicidality Tracking Scale (S-STS)

The standard version of the S-STS^[28] is a 16-item scale that assesses the seriousness of suicidality phenomena on a Likert-type scale (0 to 4) ranging from 0 = "not at all" to 4 = "extremely". It also assesses the frequency of key phenomena and the overall time spent in suicidality. The standard version is available in identical clinician- and subject-rated formats. The S-STS accommodates a wide range of time frames. In clinical trials, the frequently used variants are "in the past week", "in the past month", "since the last visit", "lifetime look back", and "in the past day".

The S-STS maps to both the C-CASA, and to all of the categories in the FDA Draft Guidance documents of both 2010 and 2012, and in addition provides coverage for all suicidal phenomena presented in the draft FDA guidance. The S-STS has been studied and validated against other instruments used for the assessment of suicidality in a study, and been shown provide at least equal sensitivity to detecting suicidal ideation and behaviors^[29]. Suicidality identified after baseline will be recorded as an adverse event.

The total score is the sum of all 16 questions and with values ranging from 0 to $64^{[29,30]}$. The response for Question 1a will be used in the total score (not the Yes/No responses for Questions 1 or 1b). If Question 14 has a score ≥ 1 , then Question 15 will be filled out. The maximum score for "How serious was each attempt?" in Question 15 will be used in the total score. If Question 12 has a score ≥ 1 , then Question 16 will be filled out. The maximum score for "How serious was each preparation?" in Question 16 will be used in the total score. If Questions 15 and/or 16 do not need to be filled out, then those responses will be set to zero. No other missing values will be imputed and if any of the first 14 questions are missing, then the total score will be set to missing.

Two additional subscale scores will be calculated^[30]:

• Suicidal Ideation:

- o If Question 5 has an individual score ≤ 1 , then the suicidal ideation subscale score is the sum of questions 2, 3, 4, and 5.
- If Question 5 has an individual score > 1, then the suicidal ideation subscale score is the sum of questions 2, 3, and 4. The suicidal ideation subscale score ranges from 0 to 13. If any of those 4 questions are missing, then the suicidal ideation subscale score will be set to missing.

Suicidal Behaviors:

- o If Question 5 has an individual score > 1, then the suicidal behaviors subscale score is the sum of questions 6, 7a, 8, and 5.
- O If Question 5 has an individual score ≤ 1 , then the suicidal behaviors subscale score is the sum of questions 6, 7a, and 8.
- O The suicidal behaviors subscale score ranges from 0 to 16. If any of those 4 questions are missing, then the suicidal behaviors subscale score will be set to missing.

The actual and change from baseline for the 16 individual item scores, suicidal ideation subscale score, suicidal behaviors subscale score, and total score will be summarized using descriptive statistics. Analysis visits Screening, Baseline, Week 2, Week 4, and Last Post-Baseline Visit will be summarized in a table. In the event the S-STS data was assessed more than once within the same day, and the results differ, the worst individual assessment from each questionnaire data will be used for this table. Any S-STS assessments that were collected more than once within the same day will be documented in the SDTM Study Data Reviewer's Guide. All numeric data and other character results collected will be presented in a subject listing.

Abnormally high post-baseline results will be additionally provided in a separate subject listing for each of the 16 questions with the following criteria:

- Scores of 3 "Very" or 4 "Extremely"
 - o Questions 2 or 13
- Scores of 2 "Moderately", 3 "Very", or 4 "Extremely"
 - O Question 1a (only if Question 1b is as "Yes")
 - o Questions 3-12 and 14
 - \circ Any Score ≥ 2 for Questions 15 and 16 (more than one response may be present for each question)

A frequency distribution table will summarize if a subject has at least one of those abnormally high results listed above for each post-baseline visit and overall.

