- 11. Human immunodeficiency virus (HIV) infection, hepatitis, or other ongoing infectious disease that the investigator considers clinically significant.
- 12. Concomitant use of antiepileptic drugs, non-steroidal anti-inflammatory drugs (except cardiac preventive acetylsalicylic acid), opioids, muscle relaxants, dextromethorphan (except low dose intermittent use for cough), tramadol, topical lidocaine, topical capsaicin, and selective norepinephrine reuptake inhibitors. Subjects are allowed to enter with a maximum of 1 allowed analgesic medication for neuropathic pain that has been taken at a stable dose for at least 1 month (30 days) prior to Visit 1. Allowed analgesics may not be *N*-methyl-D-aspartate receptor ligands, must be non-opioid and non-sedative and must not interfere with subjects' pain reporting (Section 8.7). Tricyclic antidepressants may be continued if designated as the single analgesic medication for the treatment of pain.
- 13. History of or current substance abuse disorder as defined by Diagnostic and Statistical Manual of Mental Disorders Fifth Edition.
- 14. Recreational and/or medicinal marijuana use within the past 6 months.
- 15. Positive urine drug screen for marijuana, opioids, benzodiazepines inconsistent with current prescriptions, or breathalyzer test for alcohol at Visit 1.
- 16. Positive urine drug screen for marijuana, opioids, any benzodiazepines inconsistent with current prescriptions, or breathalyzer test for alcohol at Visit 2.
- 17. Sensitivity to, allergy to, or concomitant use of *N*-methyl-D-aspartate receptor ligands including ketamine, amantadine, dextromethorphan (except low dose intermittent use for cough), memantine, methadone, dextropropoxyphene, and/or ketobemidone.
- 18. Amputations of lower extremities (toe amputation is allowed).

- 19. Any condition, including serious medical conditions that could interfere with the ability of the subject to participate in the study or could confound study assessments.
- 20. Subjects with hypersensitivity to multiple medications, in the opinion of the investigator.
- 21. Subjects who meet the criteria for suicidal intent, plan, and/or behavior by scoring 3 or 4 on Questions 2 or 13, or 2 or higher on any Question 1a (only if 1b is coded YES), 3, 4, 5, 6, 7, 8, 9, 10, 11, 12, or 14 based on the S-STS at Visit 1 or Visit 2.

Waivers to the exclusion criteria will NOT be allowed.

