12.6.5 Suicidal Ideation

Subjects with suicidal ideation or behavior will be identified with the S-STS.

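### The only S-STS table that counts subjects applies a severity threshold the protocol does not set, so subjects with only low-scored endorsements are not counted by arm

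*SAP*

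**What the plan says.** The S-STS is a named safety endpoint (Protocol 5.3.2). For its analysis, Protocol 12.6.5 has one sentence: "Subjects with suicidal ideation or behavior will be identified with the S-STS". It gives no score threshold and names no table. Protocol 9.3.6 and SAP 10.6.1 both add that suicidality found after baseline is recorded as an adverse event.

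SAP 10.6.1 scores each of 16 items from 0 (not at all) to 4 and plans four outputs:

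- descriptive statistics of item, subscale and total scores, with changes from baseline (Table 14.3.5.8.1);
- a full subject listing (16.2.9.5);
- a listing of abnormally high post-baseline results (14.3.5.8.3);
- one count table built on the same results (14.3.5.8.2): "A frequency distribution table will summarize if a subject has at least one of those abnormally high results listed above for each post-baseline visit and" across all visits combined.

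Abnormally high means 3 or 4 on Questions 2 or 13; 2 or more on Question 1a (only if 1b is Yes), Questions 3 to 12 and Question 14; and 2 or more on "Questions 15 and 16 (more than one response may be present for each question").

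Exclusion criterion 21 (Protocol 7.2) reads: "Subjects who meet the criteria for suicidal intent, plan, and/or behavior by scoring 3 or 4 on Questions 2 or 13, or 2 or higher" for Question 1a (same condition), 3 to 12, or 14.

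The SAP also uses a lower trigger. A score of 1 or more on Question 14 opens Question 15, and 1 or more on Question 12 opens Question 16. The seriousness answers then enter the total: "The maximum score for 'How serious was each attempt?' in Question 15 will be used in the total score", with a parallel rule for Question 16. SAP 4.7, which lists departures from the protocol, mentions no S-STS threshold.

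**The concern.** The count table takes over cut-offs written to decide who may enter the study. Protocol 12.6.5 asks a different question after baseline: which subjects show suicidal ideation or behavior at all. By the SAP's own scoring a 1 is not absence. Zero is the absence category, and a 1 on Question 12 or 14 is enough to require details of the preparation or attempt.

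At stake is how the report will be read. A reader will tend to take the single S-STS subject count as the suicidality result by arm. It can show no subjects in an arm where items were endorsed at low scores. It can also sit beside a suicidality adverse event for a subject it does not count, because the adverse event rule has no score threshold.

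**Working it through.** **1. The plan's own score ranges.** Using the SAP 10.6.1 rules:

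- Total: 16 items x 4 = 64 (SAP: 64).
- Ideation subscale: Questions 2, 3 and 4 give 3 x 4 = 12, and Question 5 enters only when it is at most 1, so 12 + 1 = 13 (SAP: 13).
- Behaviors subscale: Questions 6, 7a and 8 give 12, and Question 5 enters when above 1, so 12 + 4 = 16 (SAP: 16).

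All three reproduce.

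**2. Cut-offs side by side.**

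| Item | Exclusion criterion 21 | SAP count table | Scores not flagged by the SAP |
|---|---|---|---|
| 2, 13 | 3 or more | 3 or more | 1, 2 |
| 1a (if 1b Yes) | 2 or more | 2 or more | 1 |
| 3 to 12, 14 | 2 or more | 2 or more | 1 |
| 15, 16 | not used | 2 or more | 1 |

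The two sets are identical for Questions 1a to 14. The SAP adds Questions 15 and 16. No item is flagged at a score of 1.

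**3. Highest scores that are still not counted.** Set every item one below its cut-off, with Question 1b = Yes and Question 7a treated as falling within Questions 3 to 12:

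- Total: 1a (1) + Q2 (2) + Q3 to Q12 (10 x 1) + Q13 (2) + Q14 (1) + Q15 (1) + Q16 (1) = 18 of 64. If 1b is not Yes, 1a is never flagged and may be 4, giving 18 - 1 + 4 = 21.
- Ideation subscale: 2 + 1 + 1 + 1 = 5 of 13.
- Behaviors subscale: 1 + 1 + 1 = 3 of 16.

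These are limits of the rule, not expected values.

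**4. Attempt and preparation items.** With Question 14 = 1 and no other item flagged, the subject is not counted when Question 15 is 0 or 1, and is counted when it is 2, 3 or 4. Question 12 with Question 16 works in the same way.

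**5. What the other outputs show.** SAP 5.3.1 includes the minimum and maximum among descriptive statistics. An endorsement at a visit summarised in Table 14.3.5.8.1 therefore shows as an item maximum of at least 1, and a rise shows as a positive maximum change. Neither says how many subjects were involved. Listing 16.2.9.5 shows every score but gives no count by arm. The TEAE tables count subjects by arm, but only for events the site recorded.

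**The case against.** The best defence is that nothing is lost. Protocol 12.6.5 says identified, not counted, and the full listing identifies every subject with a non-zero score. Item maxima reveal endorsements by arm. Adverse event recording provides a subject count. The table's title announces abnormal results, so a zero in it would be a true statement about abnormal results. The cut-offs are also not arbitrary: criterion 21 describes them as criteria for suicidal intent, plan and/or behavior. Because it applies at Visits 1 and 2 without waivers, an eligible subject who crosses one of them later on Questions 1a to 14 has newly crossed it.

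Much of this stands, and it rules out three stronger readings that a reader might infer:

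- That the SAP omits a count the protocol requires. The protocol requires identification only.
- That any attempt or preparation scored 1 is missed. A seriousness score of 2 or more on Question 15 or 16, or another flagged item, brings the subject in.
- That low-scored suicidality disappears from the report. It is in the listing, reflected in the maxima, and in the TEAE tables if recorded.

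What the defence does not supply is a count by arm, from the S-STS itself, of subjects with new ideation or behavior. The label in criterion 21 covers intent, plan and behavior, while Protocol 12.6.5 also names ideation. The adverse event count depends on what each site recorded.

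**Conclusion.** The point holds as a reporting gap. The one S-STS table that counts subjects uses a severity threshold absent from Protocol 12.6.5 and not declared in SAP 4.7. It leaves out subjects whose only post-baseline endorsements are 1 (or 1 to 2 on Questions 2 and 13). This includes a 1 on Question 12 or 14, unless Question 16 or 15 respectively is 2 or more or another item is flagged.

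The size can be stated only as the reach of the rule: up to 18 of 64 in total with Question 1b = Yes (21 otherwise), 5 of 13 on ideation and 3 of 16 on behaviors. A reader might want to infer an under-reported rate, but the documents give no S-STS score distribution, so neither the number of subjects affected nor any difference between arms can be derived. The conclusion rests on reading a score above 0 as presence, which the scale anchor and the triggers for Questions 15 and 16 support. It does not question the eligibility cut-offs. All safety summaries are descriptive, so no test is affected; this is a cheap improvement.

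**What to change.** In SAP 10.6.1 and Table 14.3.5.8.2, keep the present rows, labelled as a high-severity subset. Add rows by arm, per post-baseline visit and overall, for subjects with:

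- (a) a suicidal ideation subscale score, as the SAP defines it, above 0 and above that subject's baseline;
- (b) a suicidal behaviors subscale score above 0 and above baseline;
- (c) Question 12 or Question 14 at 1 or more and above baseline.

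Using the SAP's subscales avoids inventing an item split: the documents assign only Questions 2 to 8 to ideation or behavior. Low scores confined to Questions 1a, 9 to 11 or 13 would stay in the full listing. If a row using Question 1a is added, keep the condition that 1b is Yes. Apply the same selection to Listing 14.3.5.8.3.

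The cost is SAP wording and a few extra rows in one table and one listing, from data already collected. The downside is that some mild or non-specific endorsements will appear; the baseline condition and the retained high-severity rows put them in context. No visit, procedure, eligibility rule or clinical decision changes.

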10.6.2 Body Weight

The subject's body weight (in kg units) will be summarized using descriptive statistics at the Screening, Baseline, Week 4, and Last Post-Baseline Visit analysis visits. The actual, change from baseline, and percent change from baseline results will be displayed in the descriptive statistics.

Subjects experiencing a \geq 7% weight gain^[31] during their last post-baseline visit will be flagged in a subject listing and summarized in a frequency distribution table.

Individual subject body weight data will be listed by the original results and units collected; as well as the results in kg units. If the data was collected in pounds, then the conversion factor will be weight in pounds x 0.454 and rounded off by one number after the decimal point. This conversion for weight to kg units will be derived in the eDC (electronic data capture) system.

10.6.3 Other Reportable Events

Other Reportable Events (OREs) are defined as reports of overdose (with or without an adverse event), abuse, dependency, inadvertent or accidental exposure, pregnancy, and unexpected therapeutic benefit should be forwarded in the same timeframe as a serious adverse event. Overdose occurs when a subject is dosed or has taken a dose greater than the intended or scheduled dose specified by the protocol.

Details and occurrences of OREs will be collected separately in a pharmacovigilance database and will be presented in a subject listing, but not summarized in a table.

11.Other Analyses

11.1 Protocol Deviations

Protocol deviations are collected during the study in the clinical trial management system (CTMS). Prior to database lock, the protocol deviations will be reviewed for the following reasons:

- Standard study terminology deviation categories assigned
- Severity (major versus minor) assigned
- If a subject should be excluded from the PP population

After database lock it may be determined that additional protocol deviations occurred, but could not be known prior to database lock. For example, a subject receiving study drug for the wrong treatment arm (i.e., a treatment arm other than the one they were randomized to). As a result, any additional protocol deviations found after database lock will be included with previous protocol deviations.

A subject listing will include the planned treatment arm, deviation category, protocol deviation, occurrence date with the corresponding study day, severity (major versus minor), and if the protocol deviation resulted in excluding a subject from the PP population. A frequency distribution table will be created to summarize only major protocol deviations by the assigned deviation categories.

12.Interim Analyses

Section 12.8 of the protocol mentioned that a potential interim analysis was being conducted, but after additional consideration no formal interim analyses will actually be performed for this study.

13.List of Planned CSR Tables, Figures, and Listings in Section 14

The following are planned summary tables, figures, and listings (TFL's). TFL's will be numbered according to the nomenclature used to support the CSR in Section 14. The final TFL numbering may be different from the SAP. No amendment will be made for changes in TFL numbering. All titles, footnotes, and headers specified in the mock TFL shells will be displayed in the produced output unless otherwise specified. Notes to programmers will not be included in the TFL's. There will be a footnote in all TFL's that includes the SAS® version number, company creating the output, program name, the date/time that the output was produced, and the dataset(s) referenced for the output. Additional footnotes may be added to help explain/support particular data values that are not displayed in the mock TFL shells. A separate mock TFL shells document will be created to support the appearances of these planned TFL's.

Number	Population*	TFL: Title		
14.1 Disposi	14.1 Disposition, Demographic, and Baseline Data Summary Tables			
14.1.1	All Subjects	Table: Analysis Populations		
14.1.2.1	Safety*	Table: Subject Disposition		
14.1.2.2	Efficacy*	Table: Subject Disposition		
14.1.2.3	PP	Table: Subject Disposition		
14.1.3.1	Safety*	Table: Demographics and Baseline Characteristics		
14.1.3.2	Efficacy*	Table: Demographics and Baseline Characteristics		

Number	Population*	TFL: Title
14.1.3.3	PP	Table: Demographics and Baseline Characteristics
14.1.4	Safety	Table: Medical History by System Organ Class and Preferred Term
14.1.5	Safety	Table: Prior Medications by ATC Class and Preferred Term
14.1.6	Safety*	Table: Questionnaire/Scale Assessments only at Screening or Baseline
14.2 Efficacy	y Data Summar	y Tables and Figures
14.2.1 Prima	ary Efficacy Dat	a
14.2.1.1.1	Efficacy*	Table: Mean Change and Percent Change from Baseline NRS Score Assessing Average Pain Intensity in the Past 24 Hours
14.2.1.1.2	PP	Table: Mean Change and Percent Change from Baseline NRS Score Assessing Average Pain Intensity in the Past 24 Hours
14.2.1.1.3	Efficacy	Table: Mean Change and Percent Change from Baseline NRS Score Assessing Average Pain Intensity in the Past 24 Hours (by Study Site)
14.2.1.1.4	Efficacy	Table: Mean Change and Percent Change from Baseline NRS Score Assessing Average Pain Intensity in the Past 24 Hours (by Age Groups)
14.2.1.1.5	Efficacy	Table: Mean Change and Percent Change from Baseline NRS Score Assessing Average Pain Intensity in the Past 24 Hours (by Gender)
14.2.1.1.6	Efficacy	Table: Mean Change and Percent Change from Baseline NRS Score Assessing Average Pain Intensity in the Past 24 Hours (by Race)
14.2.1.1.7	Efficacy	Table: Mean Change and Percent Change from Baseline NRS Score Assessing Average Pain Intensity in the Past 24 Hours (by Ethnicity)
14.2.1.1.8	Efficacy*	Table: Mean Change and Percent Change from Baseline NRS Score Assessing Average Pain Intensity in the Past 24 Hours (by Concomitant Analgesic Medications)
14.2.1.1.9	Efficacy	Figure: Mean Change from Baseline NRS Score Assessing Average Pain Intensity in the Past 24 Hours
14.2.1.2.1.1	Efficacy*	Table: Analysis of Covariance Model for Mean Change from Baseline NRS Score Assessing Average Pain Intensity in the Past 24 Hours (Observed Data)
14.2.1.2.1.2	PP	Table: Analysis of Covariance Model for Mean Change from Baseline NRS Score Assessing Average Pain Intensity in the Past 24 Hours (Observed Data)

Number	Population*	TFL: Title
14.2.1.2.2	Efficacy	Table: Analysis of Covariance Model for Mean Change from Baseline NRS Score Assessing Average Pain Intensity in the Past 24 Hours (Model-Based Missing Data Imputation)
14.2.1.2.3	Efficacy	Table: Analysis of Covariance Model for Mean Change from Baseline NRS Score Assessing Average Pain Intensity in the Past 24 Hours (LOCF Missing Data Imputation)
14.2.1.2.4	Efficacy	Table: Analysis of Covariance Model for Mean Change from Baseline NRS Score Assessing Average Pain Intensity in the Past 24 Hours (BOCF Missing Data Imputation)
14.2.1.2.5	Efficacy	Table: Analysis of Covariance Model for Mean Change from Baseline NRS Score Assessing Average Pain Intensity in the Past 24 Hours (BOCF Rescue Medication Data Imputation)
14.2.1.2.6	Efficacy*	Table: Analysis of Covariance Model for Mean Change from Baseline NRS Score Assessing Average Pain Intensity in the Past 24 Hours (Concomitant Analgesic Medications)
14.2.1.3.1	Efficacy	Table: Mixed Effects Repeated Measures Model for Mean Change from Baseline NRS Score Assessing Average Pain Intensity in the Past 24 Hours
14.2.1.3.2	PP	Table: Mixed Effects Repeated Measures Model for Mean Change from Baseline NRS Score Assessing Average Pain Intensity in the Past 24 Hours
14.2.1.4.1	Efficacy*	Table: Responder Status Endpoints Based on Mean NRS Score Assessing Average Pain Intensity in the Past 24 Hours
14.2.1.4.2	Efficacy	Figure: Percentage-Reduction from Baseline at Week 4 for Mean NRS Score Assessing Average Pain Intensity in the Past 24 Hours
14.2.1.5.1	Efficacy	Table: Number of Days to Responder Status Based on Mean NRS Score Assessing Average Pain Intensity in the Past 24 Hours
14.2.1.5.2	Efficacy	Figure: Probability of Number of Days to Responder Status Based on Mean NRS Score Assessing Average Pain Intensity in the Past 24 Hours
14.2.1.6.1	Efficacy	Table: Number of Days to Sustained Pain Reduction Based on Mean NRS Score Assessing Average Pain Intensity in the Past 24 Hours
14.2.1.6.2	Efficacy	Figure: Probability of Number of Days to Sustained Pain Reduction Based on Mean NRS Score Assessing Average Pain Intensity in the Past 24 Hours
14.2.1.7.1	Efficacy	Figure: Boxplots of Weekly Mean Change from Baseline NRS Score Assessing Average Pain Intensity in the Past 24 Hours and Average Rescue Medication Taken (g/day)

Number	Population*	TFL: Title
14.2.1.7.2	Efficacy	Figure: Scatter Plots of Weekly Mean Change from Baseline NRS Score Assessing Average Pain Intensity in the Past 24 Hours and Average Rescue Medication Taken (g/day)
14.2.2 – 14.2	2.10 Secondary 1	Efficacy Data
14.2.2.1	Efficacy*	Table: Mean Change and Percent Change from Baseline NRS Score Assessing Worst Pain Intensity in the Past 24 Hours
14.2.2.2	Efficacy*	Table: Analysis of Covariance Model for Mean Change from Baseline NRS Score Assessing Worst Pain Intensity in the Past 24 Hours
14.2.2.3	Efficacy	Table: Mixed Effects Repeated Measures Model for Mean Change from Baseline NRS Score Assessing Worst Pain Intensity in the Past 24 Hours
14.2.2.4	Efficacy	Figure: Mean Change from Baseline NRS Score Assessing Worst Pain Intensity in the Past 24 Hours
14.2.3.1	Efficacy*	Table: Mean Change and Percent Change from Baseline NRS Score Assessing Average Pain upon Walking Intensity in the Past 24 Hours
14.2.3.2	Efficacy*	Table: Analysis of Covariance Model for Mean Change from Baseline NRS Score Assessing Average Pain upon Walking Intensity in the Past 24 Hours
14.2.3.3	Efficacy	Table: Mixed Effects Repeated Measures Model for Mean Change from Baseline NRS Score Assessing Average Pain upon Walking Intensity in the Past 24 Hours
14.2.3.4	Efficacy	Figure: Mean Change from Baseline NRS Score Assessing Average Pain upon Walking Intensity in the Past 24 Hours
14.2.4.1	Efficacy*	Table: Descriptive Statistics for Patient Global Impression of Change
14.2.4.2	Efficacy	Table: Frequency Distributions for Patient Global Impression of Change
14.2.5.1	Efficacy	Table: Change from Baseline Short-Form McGill Pain Questionnaire
14.2.5.2	Efficacy	Table: Analysis of Covariance Model for Change from Baseline Short-Form McGill Pain Questionnaire
14.2.6.1	Efficacy	Table: Change from Baseline Norfolk Quality of Life Questionnaire - Diabetic Neuropathy
14.2.6.2	Efficacy	Table: Analysis of Covariance Model for Norfolk Quality of Life Questionnaire - Diabetic Neuropathy
14.2.7.1	Efficacy	Table: Change from Baseline Insomnia Severity Index
14.2.7.2	Efficacy	Table: Frequency Distributions for Insomnia Severity Index

Number	Population*	TFL: Title
14.2.7.3	Efficacy	Table: Shifts from Baseline Insomnia Severity Index
14.2.7.4	Efficacy	Table: Analysis of Covariance Model for Insomnia Severity Index
14.2.8.1	Efficacy*	Table: Change from Baseline Hospital Anxiety and Depression Scale
14.2.8.2	Efficacy*	Table: Frequency Distributions for Hospital Anxiety and Depression Scale
14.2.8.3	Efficacy	Table: Shifts from Baseline Hospital Anxiety and Depression Scale
14.2.8.4	Efficacy*	Table: Analysis of Covariance Model for Hospital Anxiety and Depression Scale
14.2.9.1	Efficacy	Table: Mean Change and Percent Change from Baseline Daily Sleep Interference Scale in the Past 24 Hours
14.2.9.2	Efficacy	Table: Analysis of Covariance Model for Mean Change from Baseline Daily Sleep Interference Scale in the Past 24 Hours
14.2.9.3	Efficacy	Table: Mixed Effects Repeated Measures Model for Mean Change from Baseline Daily Sleep Interference Scale in the Past 24 Hours
14.2.9.4	Efficacy	Figure: Mean Change from Baseline Daily Sleep Interference Scale in the Past 24 Hours
14.2.10.1	Efficacy	Table: Change from Baseline Brief Pain Inventory for Diabetic Peripheral Neuropathy
14.2.10.2	Efficacy	Table: Analysis of Covariance Model for Brief Pain Inventory for Diabetic Peripheral Neuropathy
14.3 Safety a	and Other Data	Summary Tables, Figures, and Listings
14.3.1 Adve	rse Event Table	s
14.3.1.1	Safety*	Table: Overall Summary of Treatment-Emergent Adverse Events
14.3.1.2	Safety*	Table: Treatment-Emergent Adverse Events by System Organ Class and Preferred Term
14.3.1.3	Safety	Table: Treatment-Emergent Adverse Events by Preferred Term
14.3.1.4	Safety	Table: Related Treatment-Emergent Adverse Events by System Organ Class and Preferred Term
14.3.1.5	Safety	Table: Treatment-Emergent Adverse Events by System Organ Class, Preferred Term, and Maximum Severity
14.3.1.6	Safety	Table: Serious Treatment-Emergent Adverse Events by System Organ Class and Preferred Term
14.3.1.7	Safety	Table: Treatment-Emergent Adverse Events Leading to Discontinuation by System Organ Class and Preferred Term

Number	Population*	TFL: Title			
14.3.2 Listin	14.3.2 Listing of Deaths, Other Serious and Significant Adverse Events				
14.3.2.1	Safety*	Listing: Serious Treatment-Emergent Adverse Events and Deaths			
14.3.2.2	Safety	Listing: Serious Adverse Events and Deaths Not Considered Treatment-Emergent			
14.3.3 Narra	tives of Deaths,	Other Serious and Certain Other Significant Adverse Events			
N/A	N/A	Provided by Clinical, if applicable			
14.3.4 Abno	rmal Laborator	y Value Listings			
14.3.4	Safety*	Listing: Abnormal Clinical Laboratory Results			
14.3.5 Safety	and Other Dat	a Tables, Figures, and Listings			
14.3.5.1.1.1	Safety	Table: Change from Baseline Clinical Laboratory Results for Hematology			
14.3.5.1.1.2	Safety	Table: Shifts from Baseline Clinical Laboratory Results for Hematology			
14.3.5.1.2.1	Safety	Table: Change from Baseline Clinical Laboratory Results for Serum Chemistry (Liver Function Tests)			
14.3.5.1.2.2	Safety	Table: Change from Baseline Clinical Laboratory Results for Serum Chemistry (Non-Liver Function Tests)			
14.3.5.1.2.3	Safety	Table: Shifts from Baseline Clinical Laboratory Results for Serum Chemistry (Liver Function Tests)			
14.3.5.1.2.4	Safety	Table: Shifts from Baseline Clinical Laboratory Results for Serum Chemistry (Non-Liver Function Tests)			
14.3.5.1.3.1	Safety	Table: Change from Baseline Clinical Laboratory Results for Urinalysis (Numeric Data)			
14.3.5.1.3.2	Safety	Table: Frequency Distributions for Clinical Laboratory Results for Urinalysis (Categorical Data)			
14.3.5.1.3.3	Safety	Table: Shifts from Baseline Clinical Laboratory Results for Urinalysis (Numeric Data)			
14.3.5.1.3.4	Safety	Table: Shifts from Baseline Clinical Laboratory Results for Urinalysis (Categorical Data)			
14.3.5.1.4	Safety*	Table: Potentially Clinically Significant Clinical Laboratory Results			
14.3.5.1.5	Safety*	Figure: eDISH Plots of Clinical Laboratory Results versus Total Bilirubin			
14.3.5.2	Safety	Table: Change from Baseline Vital Sign Measurements			
14.3.5.3.1	Safety	Table: Change from Baseline Electrocardiogram Parameter Results			

Number	Population*	TFL: Title
14.3.5.3.2	Safety	Table: Frequency Distributions for Electrocardiogram Interpretations
14.3.5.3.3	Safety	Table: Shifts from Baseline Electrocardiogram Interpretations
14.3.5.3.4	Safety*	Table: Frequency Distributions for Abnormally High QTcF Interval Results
14.3.5.4	Safety	Table: Study Drug Treatment Compliance and Exposure
14.3.5.5	Safety	Table: Rescue Medication
14.3.5.6.1	Safety	Table: Concomitant Medications by ATC Class and Preferred Term
14.3.5.6.2	Safety	Table: Concomitant Analgesic Medications by ATC Class and Preferred Term
14.3.5.7	Safety	Listing: Change to Abnormal Post-Baseline Physical Examinations
14.3.5.8.1	Safety	Table: Change from Baseline Sheehan Suicidality Tracking Scale
14.3.5.8.2	Safety	Table: Frequency Distributions for Abnormal Post-Baseline Sheehan Suicidality Tracking Scale Results
14.3.5.8.3	Safety	Listing: Abnormal Post-Baseline Sheehan Suicidality Tracking Scale Results
14.3.5.9	Safety	Table: Body Weight (kg)
14.3.5.10	Safety	Table: Major Protocol Deviations

^{*} Denotes a table that will be provided in the topline analyses after database lock.

14.List of Planned CSR Appendices in Section 16.2

The following are planned appendix listings used to support the CSR in Section 16.2. All subjects will be provided regardless of their randomized/treated status. The same details mentioned in the planned TFL's in Section 13 will be applied to the planned appendices.

Number	Appendix Title		
